To understand barriers and facilitators to implementation and adoption of the NOHARM intervention by inpatient care teams, we will conduct interviews with at least 1, but up to 2-3 key inpatient stakeholders from each surgical practice at least three months after their practice's go-live. We will conduct between 32 (1 interview per practice) and 96 (3 interviews per practice) interviews in total.

We will recruit participants to these interviews via email-based invitations to clinical stakeholders with whom we already have relationships (e.g., nursing managers, nursing education specialists, clinical nurse specialists, and charge nurses). These video-based interviews will last 30-45 minutes and be semi-structured to gather data corresponding to the 5 Consolidated Framework for Implementation Research (CFIR) 2.0 domains: 1) innovation characteristics, 2) outer setting, 3) inner setting, 4) key roles and characteristics, and 5) implementation process. We will make adaptations to the interview guide as needed to explore salient topics. All participants will provide verbal consent to participate. Participants will receive \$50 remuneration for participating in the interview, which will be given via payroll. All audio recordings will be transcribed and de-identified.

Analysis:

We will use a rapid analysis approach to summarize transcripts by summarizing each interview transcript under domain labels, corresponding to the interview questions. Individual summaries will be compiled into a Data Matrix to allow for comparison across practices and identify emergent themes. Using a rapid analytic approach will allow us to share ongoing findings at team meetings so that findings may be used to refine intervention implementation for later tranches. The data matrix domains may later be mapped back to to the CFIR constructs or domains the questions were designed to address so that emergent themes can be organized using the CFIR model. Constructs may also be assigned a numeric, valence rating for each practice to determine the strength of different barriers and facilitators across practices.

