We will recruit inpatient allied health nursing leaders (e.g., nurse supervisors, nurse managers, interim nurse managers, clinical nurse specialists, nursing education specialists) from all 32 clinical practices participating in the trial. We will recruit up to 90 allied health nursing leaders. Nursing leaders may be recruited in person by members of our implementation team and given the opportunity to complete the survey and turn it in in person or mail back to our team via intra-clinic mail, depending on what they prefer. For those who complete the survey online, we will email them an invitation to complete the survey along with an embedded link to complete the online version (created using Qualtrics or RedCap). Completion of the survey will be taken as a form of assent. Nursing leaders may also be recruited by phone and asked to provide answers to the survey questions via a short (< 7 minute phone call) that the study team member records in the web-based database housing the survey (e.g., RedCap, Qualtrics). Those who complete the survey will receive remuneration in the form of \$35 added to their paycheck, to compensate busy nursing leaders for their time.

Analysis:

All paper survey responses will be entered into the web-based platform (Qualtrics or RedCap) used to collect responses from the web-based version of the survey for those who choose to complete the survey online. We will calculate descriptive statistics from this survey at the site level (e.g., Rochester, Arizona, Florida, Eau Claire, La Crosse, and Mankato). The survey responses will help us identify sites who's leadership is more or less enthusiastic about the intervention and the prospect of the intervention being sustained in some form upon study determination. These findings will complement findings from the stakeholder surveys that seek to identify specific barriers and facilitators to implementation of the intervention on inpatient nursing units.

Inpatient Epic Reports:

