Using procedures like those of Aim 1, we will create automated Epic reports that summarize care team fidelity to the NOHARM intervention. Specifically, we will use these reports to identify the proportion of NOHARM patients who are discharged from a practice with NPPC selections documented in flowsheet rows and the proportion of patients for which at least some of the Healing After Surgery education listed in the Education Tab has been delivered. We will then rank order practices based on the proportion of patients who did not have NPPC selections in their chart at the time of surgery, but were discharged with NPPC selections, and the proportion of patients who had at least some Healing After Surgery education delivered by the time of discharge to identify the top 10 and bottom 10 performing practices interviewed. The proportion of patients discharged with NPPC selections is a good proxy for inpatient care team fidelity because this data point can be reliably captured and Healing After Surgery education points auto-populate for all patients, so we can evaluate whether they have been completed or not.

Analysis: After, we have identified the practices with the highest and lowest fidelity, we will create a new data matrix with the qualitative interview data from the 10 highest and lowest fidelity practices and identify differences in themes between the highest and lowest performing practices organized according to CFIR constructs. We will also compare the CFIR construct ratings between high and low fidelity sites to determine whether ratings (perceived barriers and facilitators pertaining to the different constructs) differentiate inpatient practices with high verus low fidelity.

Physical and Occupational Therapy

To understand barriers and facilitators to implementation and adoption of the NOHARM intervention by physical and occupational therapy teams, we will administer an anonymous web-based survey (RedCAP). The survey will take approximately 10 minutes to complete and consist of multiple-choice questions along with a few open-ended questions for therapists to provide additional feedback if they wish. We will ask staff which Mayo Clinic location they work at, but no other identifying information will be collected.

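### Comparing CFIR ratings only between two extreme fidelity groups makes less use of 32 practices than a rank correlation over all of them would

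*Protocol*

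**What the plan says.** All statements are in the protocol under Aim 3.

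- **Coverage of interviews** (Inpatient Care Team Interviews): the team plans "interviews with at least 1, but up to 2-3 key inpatient stakeholders from each surgical practice", and gives the total as "We will conduct between 32 (1 interview per practice) and 96 (3 interviews per practice) interviews in total". The survey section also counts 32 practices ("from all 32 clinical practices participating in the trial").
- **Ratings** (same section, Analysis): "Constructs may also be assigned a numeric, valence rating for each practice to determine the strength of different barriers and facilitators across practices". The rating is optional, but where it is made its unit is the practice.
- **Fidelity** (Inpatient Epic Reports): "we will create automated Epic reports that summarize care team fidelity to the NOHARM intervention". Two proportions are used for ranking. One is patients without selections at surgery who were discharged with them; the other is patients with at least some of the education delivered by discharge.
- **Grouping** (same section): the ranking serves to "identify the top 10 and bottom 10 performing practices interviewed". A new theme matrix is built from those two sets of 10.
- **Numeric comparison** (same section, Analysis): the team will also "compare the CFIR construct ratings between high and low fidelity sites", to see whether ratings differentiate the two.

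The protocol describes no use of the middle practices in the numeric comparison and gives no reason for leaving them out. It states no test, alpha, effect size or power for it.

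**The concern.** An extreme-group contrast pays when measuring the middle of the range is expensive, and it suits the reading of transcripts, where a sharp contrast helps and in-depth work is saved. The numeric comparison is different. It uses one number per construct per practice, set against a fidelity measure that automated reports supply for every practice. Turning that measure into high or low discards the order within each group and everything between the groups.

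The practice is the unit, so there are at most 32 data points. In so small a sample, an avoidable loss of information affects which constructs are seen to track fidelity. A two-group contrast also gives no direct estimate of how ratings move with fidelity across its range, although Aim 3 sets out to test for associations.

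**Working it through.** **1. The protocol's own counts.** The practices listed in Figure 1, by tranche, are 9 + 6 + 5 + 7 + 5 = 32. The interview total is 32 × 1 = 32 to 32 × 3 = 96, as stated. The groups keep 10 + 10 = 20 practices, so 32 − 20 = 12 (12/32 = 37.5%) are unused if every practice is interviewed.

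**2. Large-sample efficiency.** With a fraction p in each tail, normal fidelity and a weak association, the efficiency of the extreme-group contrast relative to analysing everyone with fidelity kept continuous is

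E(p) = 2p · [φ(c)/p]², where c is the upper-p normal quantile.

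For p = 10/32 = 0.3125: c = 0.489 and φ(c) = 0.354, so E = 2 × 0.3125 × (0.354/0.3125)² ≈ 0.80.

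For comparison, E(0.27) ≈ 0.81 and E(0.50) ≈ 0.64. Among two-group designs, 10 of 32 per tail is therefore close to the best available. The step that costs information is the grouping itself.

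**3. Power at 32 practices.** The protocol gives no figure to reproduce here, so the following are assumptions: fidelity and rating bivariate normal, two-sided alpha 0.05, all 32 practices interviewed and rated. Results are from 20,000 simulated samples per row.

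| True correlation | Pearson, 32 | t-test, 10 v 10 | Spearman, 32 | Mann-Whitney, 10 v 10 | t-test, 16 v 16 |
|---|---|---|---|---|---|
| 0.3 | 0.39 | 0.31 | 0.36 | 0.27 | 0.26 |
| 0.4 | 0.64 | 0.51 | 0.58 | 0.46 | 0.44 |
| 0.5 | 0.85 | 0.73 | 0.80 | 0.69 | 0.65 |
| 0.6 | 0.97 | 0.90 | 0.94 | 0.87 | 0.83 |

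At a true correlation of zero, all five methods reject in 4% to 5% of samples, so the comparison is fair. The gap between the all-practice correlation and the matching 10 v 10 test is about 7 to 13 percentage points. Simulation error moves the second decimal by about one unit at most.

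**4. Coarse ratings.** A valence rating will have few levels. With the simulated rating rounded to −2 to +2, Pearson against the t-test gives 0.60 v 0.48 at 0.4 and 0.82 v 0.69 at 0.5. Spearman against Mann-Whitney gives 0.55 v 0.44 and 0.77 v 0.65. The gap remains.

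**5. Where the loss arises.** Putting the 12 middle practices back into a high/low split (16 v 16) lowers t-test power from 0.51 to 0.44 at 0.4, and from 0.73 to 0.65 at 0.5. The middle practices add information only if fidelity is analysed as a continuous or ranked variable.

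**The case against.** **No test is specified.** The protocol says only that ratings will be compared, and the method for a secondary mixed-methods comparison may sit in an SAP that is not shown. That stands against treating the power figures as a failing of a stated test. It does not remove the point, because the grouping and its size are fixed in the protocol.

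**The ratings may not exist for all practices.** They are optional, and the firm commitment to organise data by CFIR construct concerns the 20 extreme practices. If rating were done only at that stage, rating 12 more would be extra work. The wording "numeric, valence rating for each practice" points to ratings for all, but the protocol does not settle it. A reader might infer that the 12 ratings are already in hand and dropped for no saving; the documents do not establish that.

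**The sentence on ratings does not repeat 10 and 10.** This is correct, but the sentence before it defines the high and low groups that way, and no other definition is offered.

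**Discarding the middle as the cause.** A reader might infer that leaving out 12 practices is what loses power. Step 5 shows otherwise for any two-group comparison.

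**Near-ties at rank 10.** A reader might infer that the result is fragile at the cut. A swap at the boundary moves a practice in or out of the comparison but, with 12 practices between the groups, not from high to low. The concern is limited.

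**The aim is descriptive.** A 10 v 10 contrast does answer whether ratings distinguish high from low practices, so it is worth keeping as illustration.

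**Conclusion.** The point holds as a moderate inefficiency in an exploratory comparison. For the numeric CFIR ratings, two extreme groups of 10 carry about 0.80 of the information in a full analysis and lose roughly 7 to 13 points of power against a correlation over 32 practices. The size rests on assumed normality, alpha 0.05, true correlations of 0.3 to 0.6, and all 32 practices being interviewed and rated; none of these is given as a planning value in the protocol.

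Nothing here makes the planned comparison invalid, and the protocol does not contradict itself on this point. Nor does the change make the analysis well powered throughout: at a correlation of 0.4 the rank correlation still reaches only 0.58. The extreme-group split remains a sound choice for the qualitative theme matrix.

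**What to change.** In Aim 3, Inpatient Epic Reports, Analysis:

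1. Keep the split into the 10 highest and 10 lowest practices for the theme matrix.
2. State that if CFIR ratings are assigned, they are assigned for all interviewed practices.
3. Report, for each construct, a rank correlation with a confidence interval between the rating and each of the two fidelity proportions, over all interviewed practices. Since no single fidelity proportion is defined, the alternative is to use the same rank that forms the split.
4. Show the 10 v 10 contrast of ratings as illustration.
5. Do not add the middle practices to a high/low split, because that lowers power.

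The cost is a few sentences of analysis text and two correlations per construct (one if the common rank is used). If ratings would otherwise be made only for the 20 extreme practices, there is also a small amount of rating work for up to 12 more. No further interviews or Epic reports are needed.

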As part of the NOHARM trial, all patients on the NOHARM registry (e.g. patients in all active clusters undergoing a qualifying procedure) receive an educational tool in their portals pre-operatively called the Healing After Surgery Guide. Ambulatory care teams are encouraged to inform patients about the Guide and encourage patients to access it. Patients are expected to review the guide and select their non-pharmacologic preferences from among 13 options. These selections automatically populate flowsheet rows in Epic and trigger other supports that prompt inpatient nurses to provide tailored education and the selected modalities as feasible. This trial is operating under a waiver of consent as previously approved by the Mayo Clinic IRB.

The ongoing NOHARM study is designed to determine the effectiveness of the NOHARM intervention (e.g. the patient education and clinical decision making and support bundle). Inevitably, the NOHARM intervention will be more effective in some practices and for some patients than in others. Reasons for this are multiple and complex, but important to understand. For example, if care teams within a surgical practice do not deliver the NOHARM intervention as intended it may appear less effective than it could be. Similarly, the same effect could be seen if patients are unable or unwilling to participate in the intervention fully. The ongoing NOHARM study is not designed to explore or make sense of these issues. Thus, it is unable to explain variation in key effectiveness outcomes. More importantly, the trial itself is unable to provide practical guidance on how to optimize the intervention to improve its potential for adoption and use by diverse surgical care teams and types of patients.

Study Objective and Aims

The objective of this follow-on study is to enrich the ongoing NOHARM pragmatic trial initiative with a mixed methods analysis of patient and care team factors that affect the routine adoption, implementation, and meaningful and sustainable use of the NOHARM intervention. To accomplish this objective, we will pursue the following aims:

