Aim 1: Explore differences in patient engagement with the NOHARM intervention, use of non-pharm modalities, and clinical outcomes by key patient demographics, including surgical procedure type, gender, and opioid abuse risk. This aim will provide information about patient characteristics that may better predict who will use and/or benefit from the NOHARM intervention and who will not.

Aim 2: Qualitatively explore patient-level factors contributing to their ability to effectively engage with the NOHARM intervention in a diverse subgroups that adopt and use the intervention as intended and those that do not, respectively. This aim will provide information that helps us explain *why* some patients tend to use and/or benefit from NOHARM and others do not.

Aim 3: Characterize, using mixed methods, the relative fidelity and sustainability of implementation of NOHARM among surgical practices and test for associations with patient engagement and clinical outcomes. This aim will provide information about the characteristics of care teams that tend to adopt and maintain use of the NOHARM intervention and those that do not. It will also provide information about whether care teams play an important role in prompting patients to engage with and benefit from the NOHARM intervention.

Participants

Participants eligible for this study will be patients on the NOHARM trial registry (e.g. patients that were automatically assigned to receive the NOHARM intervention as part of their surgical care) and/or their charts and members of their care teams, including nurses, doctors, physical therapists, nurse practitioners and physician assistants, and medical assistants.

Aim 1 will exclusively use existing, Epic-based datasets and reports to conduct passive, observational secondary analyses using existing variables from medical record. For this aim, no participants will be directly contacted. For Aims 2 and 3 we will use qualitative methods and will recruit a purposeful sample of patient and care team member participants, respectively. Details about these procedures and samples are outlined below.

Procedure and Methods

Aim 1: Explore differences in patient engagement with the NOHARM intervention, non-pharm modalities, and clinical outcomes by key patient demographics, including surgical procedure type, gender, and opioid abuse risk.

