We will create Epic reports that combine all key variables for this aim. Specifically, reports will list all patients on the NOHARM registry, along with their age, sex, procedure type, surgeon, surgery location, insurance type, home zip code (for rurality), portal status (user vs non-user) and whether the patient interacted with the Healing After Surgery Guide. For patients that interacted with the Guide, the reports will also include opioid abuse risk (calculated from patient-reported outcomes) and non-pharm selections made, if any. Finally, reports will also include non-pharm modalities used as self-reported in post-operative surveys and include all patients that have completed the post-op follow-up period.

We will construct a "patient engagement and fidelity" variable based on data existing in the reports (made nonpharm selections y/n, used non-pharm modality in recovery y/n) and calculate these for all patients. We will use the distribution of patients by this variable to assess for correlations with clinical outcomes collected in the NOHARM trial (e.g. changes in pain and function). We will also explore the distribution of the variable within different demographic subgroups. If important contributors to patient engagement and fidelity are identified by this process, we will conduct adjusted analyses as appropriate.

Aim 2: Qualitatively explore determinants of patients' ability to effectively engage with the NOHARM intervention in a diverse subset of patients that adopt and use the intervention as intended and those that do not, respectively.

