disciplines (e.g. not necessarily 2 patients from each discipline and location) across the entire sample (at least 42 total interviews throughout the study duration). We will transcribe all recordings for analysis. We will first use a rapid analytic approach to analyze transcripts by summarizing each interview transcript under domain labels, corresponding to the interview questions. Individual summaries will be compiled into a Data Matrix to allow for comparison across interviews and identify emergent themes and differences between groups of patients, who vary in their level of engagement with the NOHARM intervention. The Rapid approach allows for ongoing learning and quick identification of any iterative improvements that could enhance the intervention for patients. The final data matrix may be uploaded to Nvivo to allow for coding and querying of codes, followed by memo summarization and discussion to arrive at consensus of themes.

Once data has been rapidly analzyed, we may return to the transcripts for more in depth analysis consisting of regular meetings, code book drafting and revision, coding of transcripts, resolving differing interpretations by consensus, running coding queries in Nvivo, memo summarization, and subsequent synthesizing into themes. We will categorize themes that characterize and distinguish high and low fidelity NOHARM engagement within and between patient groups, and may explore other key topic areas that emerge upon reviewing the qualitative data.

Aim 3: Characterize, using mixed methods, barriers and facilitators to implementing the NOHARM intervention and its potential for sustainability among surgical care teams and test for associations with patient engagement and clinical outcomes.

This aim will provide information about barriers and facilitators to implementation of NOHARM experienced by different clinical care team members (e.g., nurses, nursing leadership, physical and occupational therapy, physical and occupational therapy leaders). Data gleaned from this aim may help us understand whether care teams play an important role in prompting patients to engage with and benefit from the NOHARM intervention.

Inpatient Care Team Interviews

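### In the inpatient part of Aim 3, chart-documented selections enter both care-team fidelity and patient engagement, so their association can be partly or wholly an artefact of the definitions

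*Protocol*

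**What the plan says.** Study Objective and Aims says that Aim 3 will characterize implementation among surgical practices and "test for associations with patient engagement and clinical outcomes". The methods heading for Aim 3 repeats this. The stated purpose includes learning whether care teams have an important part in getting patients to engage.

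The only engagement variable defined is under Aim 1 in Procedure and Methods. It has two yes/no items: "made nonpharm selections y/n, used non-pharm modality in recovery y/n". The first item has no time point and does not say who entered the selection. The same section lists "non-pharm selections made, if any" among the data for patients who interacted with the Guide.

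Background and Introduction describes patients choosing in the Guide, which they receive before surgery, and continues: "These selections automatically populate flowsheet rows in Epic and trigger other supports".

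Inpatient Epic Reports, under Aim 3, uses three fidelity quantities:
- the share of patients discharged with selections in the flowsheet rows, which is reported and defended: "The proportion of patients discharged with NPPC selections is a good proxy for inpatient care team fidelity";
- for ranking, the proportion with no selections at surgery who were discharged with them, denominator not stated;
- also for ranking, the proportion with at least some Healing After Surgery education delivered by discharge.

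**The concern.** The presence of selections in the chart is a component of both sides of the fidelity-engagement comparison. A patient who chooses at home raises the defended fidelity proxy and the engagement variable together, with no ward action. A practice whose patients are active before surgery then looks like a practice whose ward team performs well.

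The ranking measure removes patients who had already chosen. Whether that removes the problem depends on two things the protocol leaves open: the denominator, and whether engagement counts selections entered during the stay. A correlation of either sign could be read as evidence on whether ward teams prompt engagement, which is the question the aim poses.

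**Working it through.** The protocol states no correlation, effect size or power for this test, so there is no figure to reproduce. The check has two parts: algebra on the definitions, then a simulation.

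**Notation.** For each practice, p is the share with selections at surgery and q is the ward's capture rate among the rest. Assume p and q are independent across practices.
- Share discharged with selections: D = p + (1 - p)q. This is also engagement counted at any time.
- Ranking measure over all patients: A = (1 - p)q.
- Ranking measure over patients without selections at surgery: q.
- Engagement counted pre-operatively: p.

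**Covariances under independence.**
- D with D: identical, so r = 1.
- D with p: Var(p)(1 - E[q]), positive.
- A with p: -E[q]Var(p), negative.
- A with D: Var(A) - E[q]Var(p), either sign.
- q with D: (1 - E[p])Var(q), positive.
- q with p: zero.

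**One case by hand.** Assume mean p = mean q = 0.30, both with SD 0.10.
- Var(A) = (0.49 + 0.01)(0.09 + 0.01) - 0.49 × 0.09 = 0.0500 - 0.0441 = 0.0059.
- Var(D) = 0.0100 + 0.0059 - 2 × 0.30 × 0.0100 = 0.0099.
- r(D, p) = 0.0070/√(0.0099 × 0.0100) = 0.70.
- r(A, p) = -0.0030/√(0.0059 × 0.0100) = -0.39.
- r(A, D) = (0.0059 - 0.0030)/√(0.0059 × 0.0099) = 0.38.
- r(q, D) = 0.0070/√(0.0100 × 0.0099) = 0.70.

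The sign of r(A, D) can flip. With mean p 0.50 (SD 0.15) and mean q 0.30 (SD 0.10), Var(A) = 0.2725 × 0.10 - 0.25 × 0.09 = 0.00475. Since E[q]Var(p) = 0.00675, the covariance is -0.0020.

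**Simulation.** The 32 practices come from the protocol; Figure 1 also counts to 9 + 6 + 5 + 7 + 5 = 32. Assumed: 200 patients per practice and 2,000 runs per scenario. The scenarios (mean p, mean q; SDs) are I (0.30, 0.30; 0.10, 0.10), II (0.15, 0.40; 0.08, 0.15) and III (0.50, 0.30; 0.15, 0.10). The two-sided 5% critical |r| for 32 practices is 0.349. Entries are mean r.

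| Fidelity | Engagement item | I | II | III |
|---|---|---|---|---|
| Discharged with selections | any time | 1.00 | 1.00 | 1.00 |
| Discharged with selections | pre-operative | 0.69 | 0.35 | 0.88 |
| Ranking, all patients | any time | 0.39 | 0.81 | -0.20 |
| Ranking, all patients | pre-operative | -0.38 | -0.24 | -0.63 |
| Ranking, non-selectors | any time | 0.70 | 0.93 | 0.44 |
| Ranking, non-selectors | pre-operative | -0.01 | 0.00 | 0.00 |

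In the last row |r| exceeds 0.349 in 5 to 6% of runs, about the nominal rate. In the second row it does so in 53 to 100% of runs.

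**Dilution by the unshared items.** Modality use (mean 0.50, SD 0.10) and education delivered (mean 0.50, SD 0.15) were drawn independently, and the two items on each side were weighted equally.
- Discharge proxy against the two-item engagement score: 0.70 to 0.79 (any time), 0.21 to 0.73 (pre-operative).
- All-patient ranking measure combined with the education rank, against the two-item score: -0.12 to +0.44 (any time), -0.11 to -0.36 (pre-operative).

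**The case against.** The strongest reply is that the ranking measure was evidently built to separate ward work from prior patient activity, and that the protocol supports reading engagement as Guide-based and therefore pre-operative. If the denominator is patients without selections at surgery, the correlation from the definitions is zero. That stands. A reader might infer that an association arises by construction under every reading, and the documents do not support that. But this pairing sets ward care against behaviour that came before it, so it cannot show that ward teams prompt engagement. The protocol also still defends the unrestricted proxy.

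Second, if engagement counts selections made during the stay, ward capture really does produce some of them. Part of the any-time correlation is then actual ward activity. That also stands. Even so, the comparison sets the capture rate against a quantity that contains it and says little about what patients go on to do.

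Third, each measure has a second, unshared item. These shrink the artefact but do not remove it.

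Fourth, the association appears only in the aim statements; the analysis described under Inpatient Epic Reports compares interview themes and CFIR ratings. Details of the model may sit in a statistical analysis plan that is not at hand. But the association is a stated objective, and the overlapping definitions are the protocol's own.

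A reader might also extend the point to all of Aim 3. That goes too far. Clinical outcomes are not built from selections, and the therapist fidelity measure uses BPA acknowledgement and smartphrase use.

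**Conclusion.** The concern holds for the inpatient fidelity-engagement association only. For the defended proxy a positive association is built in: 1.00 with any-time selections and 0.35 to 0.88 with pre-operative selections, before dilution. For the ranking measure the artefact can be positive, negative or absent (-0.63 to +0.93). The one pairing that removes it cannot answer the aim's question about ward teams.

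The signs that the algebra fixes follow from the definitions and from independence of p and q. The sizes, and the sign for the all-patient ranking measure against any-time engagement, rest on assumed selection rates, between-practice spread and practice size, none of which the protocol gives. It should be corrected before the association is interpreted, but it does not undermine the rest of the aim.

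**What to change.** For the inpatient fidelity-engagement test, Aim 3 should state that:
- engagement is self-reported modality use in the post-operative surveys, without the made-selections item;
- the fidelity exposure is the proportion of patients with at least some Healing After Surgery education delivered by discharge;
- if a selections-based fidelity measure is kept, it is capture among patients without selections at surgery, with that denominator written down;
- the analysis adjusts for, or is stratified by, whether the patient had selections at surgery. Selections trigger ward supports, so they may drive both education delivered and later modality use;
- any association between selections-based fidelity and selections-based engagement is reported descriptively only, with a note that the measures share an item.

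The sentence defending the discharge proxy should be reconciled with the measure used for ranking.

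The cost is a few sentences and no new data, since the reports already hold these variables. The downside is that the engagement side then rests on survey respondents only.
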